## **CLINICAL STUDY REPORT**

A Signatory Investigator must be selected to sign the clinical study report.

For each CSR related to this protocol, the following criteria will be used to select the signatory investigator:

- External Principal Investigator designated at protocol development
- National Coordinating Investigator
- Study Steering Committee chair or their designee
- Participant recruitment (eg, among the top quartile of enrollers)
- Involvement in trial design
- Regional representation (eg, among top quartile of enrollers from a specified region or country)
- Other criteria (as determined by the study team)

## **SCIENTIFIC PUBLICATIONS**

The data collected during this study are confidential and proprietary to Sponsor or designee. Any publications or abstracts arising from this study must adhere to the publication requirements set forth in the clinical trial agreement (CTAg) governing [Study site or Investigator] participation in the study. These requirements include, but are not limited to, submitting proposed publications to Sponsor or designee at the earliest practicable time prior to submission or presentation and otherwise within the time period set forth in the CTAg.

Scientific Publications (such as abstracts, congress podium presentations and posters, and manuscripts) of the study results will be a collaborative effort between the study Sponsor and the external authors. No public presentation or publication of any interim results may be made by any principal investigator, sub-investigator or any other member of the study staff without the prior written consent of the Sponsor.

Authorship of publications at BMS is aligned with the criteria of the International Committee of Medical Journal Editors (ICMJE, [www.icmje.org](http://www.icmje.org)). Authorship selection is based upon significant contributions to the study (ie, ICMJE criterion #1). Authors must meet all 4 ICMJE criteria for authorship:

- 1) Substantial intellectual contribution to the conception or design of the work; or the acquisition of data (ie, evaluable subjects with quality data), analysis, or interpretation of data for the work (eg, problem solving, advice, evaluation, insights and conclusion); AND
- 2) Drafting the work or revising it critically for important intellectual content; AND
- 3) Final approval of the version to be published; AND
- 4) Agreement to be accountable for all aspects of the work in ensuring that questions related to the accuracy or integrity of any part of the work are appropriately investigated and resolved.

Those who make the most significant contributions, as defined above, will be considered by BMS for authorship of the primary publication. Sub-investigators will generally not be considered for authorship in the primary publication. Geographic representation will also be considered.

Authors will be listed by order of significant contributions (highest to lowest), with the exception of the last author. Authors in first and last position have provided the most significant contributions to the work.

For secondary analyses and related publications, author list and author order may vary from primary to reflect additional contributions.

**APPENDIX 3 ADVERSE EVENTS AND SERIOUS ADVERSE EVENTS:  
DEFINITIONS AND PROCEDURES FOR RECORDING,  
EVALUATING, FOLLOW UP AND REPORTING**

**ADVERSE EVENTS**

Adverse Event Definition:
An Adverse Event (AE) is defined as any new untoward medical occurrence or worsening of a preexisting medical condition in a clinical investigation participant administered study treatment and that does not necessarily have a causal relationship with this treatment.
An AE can therefore be any unfavorable and unintended sign (such as an abnormal laboratory finding), symptom, or disease temporally associated with the use of study treatment, whether or not considered related to the study treatment.
Events Meeting the AE Definition

 
Any abnormal laboratory test results (hematology, clinical chemistry, or urinalysis) or results from other safety assessments (eg, ECG, radiological scans, vital signs measurements), including those that worsen from baseline, considered clinically significant in the medical and scientific judgment of the investigator. Note that abnormal lab tests or other safety assessments should only be reported as AEs if the final diagnosis is not available. Once the final diagnosis is known, the reported term should be updated to be the diagnosis.
 
Exacerbation of a chronic or intermittent pre-existing condition including either an increase in frequency and/or intensity of the condition.
 
New conditions detected or diagnosed after study intervention administration even though it may have been present before the start of the study.
 
Signs, symptoms, or the clinical sequelae of a suspected drug-drug interaction.
 
Signs, symptoms, or the clinical sequelae of a suspected overdose of either study intervention or a concomitant medication. Overdose, as a verbatim term (as reported by the investigator), should not be reported as an AE/SAE unless it is an intentional overdose taken with possible suicidal/self-harming intent. Such overdoses should be reported regardless of sequelae and should specify "intentional overdose" as the verbatim term
 

Events NOT Meeting the AE Definition

 
Medical or surgical procedure (eg, endoscopy, appendectomy): the condition that leads to the procedure is the AE.
 
Situations in which an untoward medical occurrence did not occur (social and/or convenience admission to a hospital).
 

**DEFINITION OF SAE**

If an event is not an AE per definition above, then it cannot be an SAE even if serious conditions are met.

## SERIOUS ADVERSE EVENTS

Serious Adverse Event (SAE) is defined as any untoward medical occurrence that, at any dose:
Results in death
Is life-threatening (defined as an event in which the participant was at risk of death at the time of the event; it does not refer to an event which hypothetically might have caused death if it were more severe)
Requires inpatient hospitalization or causes prolongation of existing hospitalization (see NOTE below)
NOTE: The following hospitalizations are not considered SAEs in BMS clinical studies: 
 
• a visit to the emergency room or other hospital department < 24 hours, that does not result in admission (unless considered an important medical or life-threatening event)
 
• elective surgery, planned prior to signing consent
 
• admissions as per protocol for a planned medical/surgical procedure
 
• routine health assessment requiring admission for baseline/trending of health status (e.g., routine colonoscopy)
 
• medical/surgical admission other than to remedy ill health and planned prior to entry into the study. Appropriate documentation is required in these cases
 
• admission encountered for another life circumstance that carries no bearing on health status and requires no medical/surgical intervention (e.g., lack of housing, economic inadequacy, caregiver respite, family circumstances, administrative reason)
 
• admission for administration of anticancer therapy in the absence of any other SAEs (applies to oncology protocols)
 

Results in persistent or significant disability/incapacity
Is a congenital anomaly/birth defect
Is an important medical event (defined as a medical event(s) that may not be immediately life-threatening or result in death or hospitalization but, based upon appropriate medical and scientific judgment, may jeopardize the participant or may require intervention [e.g., medical, surgical] to prevent one of the other serious outcomes listed in the definition above.) Examples of such events include, but are not limited to, intensive treatment in an emergency room or at home for allergic bronchospasm; blood dyscrasias or convulsions that do not result in hospitalization.) Potential drug induced liver injury (DILI) is also considered an important medical event. (See Section 9.2.7 for the definition of potential DILI.)

Pregnancy and potential drug induced liver injury (DILI) must follow the same transmission timing and processes to BMS as used for SAEs (see [section 9.2.5](#) for reporting pregnancies).

## EVALUATING AES AND SAES

### Assessment of Causality

- The investigator is obligated to assess the relationship between study intervention and each occurrence of each AE/SAE.
- A “reasonable possibility” of a relationship conveys that there are facts, evidence, and/or arguments to suggest a causal relationship, rather than a relationship cannot be ruled out.
- The investigator will use clinical judgment to determine the relationship.
- Alternative causes, such as underlying disease(s), concomitant therapy, and other risk factors, as well as the temporal relationship of the event to study intervention administration will be considered and investigated.
- The investigator will also consult the Investigator’s Brochure (IB) and/or Product Information, for marketed products, in his/her assessment.
- For each AE/SAE, the investigator must document in the medical notes that he/she has reviewed the AE/SAE and has provided an assessment of causality.
- There may be situations in which an SAE has occurred and the investigator has minimal information to include in the initial report to Sponsor. However, it is very important that the investigator always make an assessment of causality for every event before the initial transmission of the SAE data to Sponsor.
- The investigator may change his/her opinion of causality in light of follow-up information and send a SAE follow-up report with the updated causality assessment.

The causality assessment is one of the criteria used when determining regulatory reporting requirements.

### Follow-up of AEs and SAEs

If only limited information is initially available, follow-up reports are required. (Note: Follow-up SAE reports must include the same investigator term(s) initially reported.)

If an ongoing SAE changes in its intensity or relationship to study treatment or if new information becomes available, the SAE report must be updated and submitted within 24 hours to BMS (or designee) using the same procedure used for transmitting the initial SAE report.

All SAEs must be followed to resolution or stabilization.

## REPORTING OF SAEs TO SPONSOR OR DESIGNEE

- SAEs, whether related or not related to study treatment, and pregnancies must be reported to BMS (or designee) immediately within 24 hours of awareness of the event.
- SAEs must be recorded on the SAE Report Form.
  - The required method for SAE data reporting is through the eCRF.
  - The paper SAE Report Form is only intended as a back-up option when the electronic data capture (EDC) system is unavailable/not functioning for transmission of the eCRF to BMS (or designee).
    - ◆ In this case, the paper form is transmitted via email or confirmed facsimile (fax) transmission
    - ◆ When paper forms are used, the original paper forms are to remain on site
- Pregnancies must be recorded on a paper Pregnancy Surveillance Form and transmitted via email or confirmed facsimile (fax) transmission

**SAE Email Address: Refer to Contact Information list.**

**SAE Facsimile Number: Refer to Contact Information list.**

**SAE Telephone Contact** (required for SAE and pregnancy reporting): Refer to Contact Information list

## APPENDIX 4 WOMEN OF CHILDBEARING POTENTIAL DEFINITIONS AND METHODS OF CONTRACEPTION

### DEFINITIONS

#### Woman of Childbearing Potential (WOCBP)

A woman is considered fertile following menarche and until becoming post-menopausal unless permanently sterile. Permanent sterilization methods include hysterectomy, bilateral salpingectomy, and bilateral oophorectomy.

#### Women in the following categories are not considered WOCBP

- Premenarchal
- Premenopausal female with 1 of the following:
  - Documented hysterectomy
  - Documented bilateral salpingectomy
  - Documented bilateral oophorectomy

Note: Documentation can come from the site personnel's review of the participant's medical records, medical examination, or medical history interview.

- Postmenopausal female
  - A postmenopausal state is defined as 12 months of amenorrhea in a woman over age 45 years in the absence of other biological or physiological causes. In addition, females under the age of 55 years must have a serum follicle stimulating hormone, (FSH) level > 40 mIU/mL to confirm menopause.

### CONTRACEPTION GUIDANCE FOR FEMALE PARTICIPANTS OF CHILD BEARING POTENTIAL

One of the highly effective methods of contraception listed below is required during study duration and until the end of relevant systemic exposure, defined as 5 months after the end of study treatment.\*

**Note: For WOCBP participants treated with BMS-986205 in this study, hormone-based contraceptives are not considered highly effective methods of contraception since potential interactions of BMS-986205 with hormonal contraceptives are not known at this time. This constraint applies to Arms C and D in this study.**

Highly Effective Contraceptive Methods That Are User Dependent
---

Failure rate of <1% per year when used consistently and correctlya
---

- |  |
|--|
| 

• Not acceptable in WOCBP participants treated with BMS-986205 in this study (Arms C and D): Combined (estrogen- and progestogen-containing) hormonal contraception associated with inhibition of ovulation/or implantation (These methods of contraception cannot be used by WOCBP participants in studies where hormonal contraception is prohibited)b

– oral (birth control pills)

 |
|--|

 
– intravaginal (vaginal birth control suppositories, rings, creams, gels)
 
– transdermal
 

 
• Not acceptable in WOCBP participants treated with BMS-986205 in this study (Arms C and D): Progestogen-only hormonal contraception associated with inhibition of ovulationb 
 
– oral
 
– injectable
 
 
 
• Not acceptable in WOCBP participants treated with BMS-986205 in this study (Arms C and D): Hormonal methods of contraception including oral contraceptive pills containing a combination of estrogen and progesterone, vaginal ring, injectables, implants and intrauterine hormone-releasing system (IUS)b,c 
 
–
 
 
 

Highly Effective Methods That Are User Independent


 
• Not acceptable in WOCBP participants treated with BMS-986205 in this study (Arms C and D): Implantable progestogen-only hormonal contraception associated with inhibition of ovulationb 
 
• Intrauterine device (IUD)c
 
• Bilateral tubal occlusion
 
 
 
• Vasectomized partner
 
 
A vasectomized partner is a highly effective contraception method provided that the partner is the sole male sexual partner of the WOCBP and the absence of sperm has been confirmed. If not, an additional highly effective method of contraception should be used.

 
• Sexual abstinence
 
 
Sexual abstinence is considered a highly effective method only if defined as refraining from heterosexual intercourse during the entire period of risk associated with the study drug. The reliability of sexual abstinence needs to be evaluated in relation to the duration of the study and the preferred and usual lifestyle of the participant.
 
 
• It is not necessary to use any other method of contraception when complete abstinence is elected.
 
• WOCBP participants who choose complete abstinence must continue to have pregnancy tests, as specified in Section 2.
 
• Acceptable alternate methods of highly effective contraception must be discussed in the event that the WOCBP participants chooses to forego complete abstinence
 

NOTES:
 
a Typical use failure rates may differ from those when used consistently and correctly. Use should be consistent with local regulations regarding the use of contraceptive methods for participants participating in clinical studies.
 
b Hormonal contraception may be susceptible to interaction with the study drug, which may reduce the efficacy of the contraceptive method. Hormonal contraception is permissible only when there is sufficient evidence that the IMP and other study medications will not alter hormonal exposures such that contraception would be ineffective or result in increased exposures that could be potentially hazardous. In this case, alternative methods of contraception should be utilized.

c Intrauterine devices and intrauterine hormone releasing systems are acceptable methods of contraception in the absence of definitive drug interaction studies when hormone exposures from intrauterine devices do not alter contraception effectiveness. The absence of such interactions is not known for BMS-986205 when administered with nivolumab. Therefore, for participants of child-bearing potential who receive these 2 medications, intrauterine hormone-releasing systems are not acceptable methods of contraception.

#### Unacceptable Methods of Contraception\*

- Male or female condom with or without spermicide. Male and female condoms cannot be used simultaneously
- Diaphragm with spermicide
- Cervical cap with spermicide
- Vaginal Sponge with spermicide
- Progestogen-only oral hormonal contraception, where inhibition of ovulation is not the primary mechanism of action
- Periodic abstinence (calendar, symptothermal, post-ovulation methods)
- Withdrawal (coitus interruptus).
- Spermicide only
- Lactation amenorrhea method (LAM)

**\* Local laws and regulations may require use of alternative and/or additional contraception methods.**

### CONTRACEPTION GUIDANCE FOR MALE PARTICIPANTS WITH PARTNER(S) OF CHILD BEARING POTENTIAL.

Male participants with female partners of childbearing potential are eligible to participate if they agree to the following during the treatment and until the end of relevant systemic exposure. This constraint applies to Arms C and D in this study.

- Inform any and all partner(s) of their participation in a clinical drug study and the need to comply with contraception instructions as directed by the investigator.
- Male participants are required to use a synthetic or latex condom during any sexual activity with WOCBP for study duration and until end of relevant systemic exposure defined as 1 month (approximately 4 weeks) after the end of study treatment. This applies even if the participant has undergone a successful vasectomy.
- Female partners of males participating in the study to consider use of effective methods of contraception until the end of relevant systemic exposure, defined as 1 month (approximately 4 weeks) after the end of treatment in the male participant.
- Male participants with a pregnant or breastfeeding partner must agree to remain abstinent from penile vaginal intercourse or use a male latex or synthetic condom during each episode of

penile penetration during the treatment and until 1 month (approximately 4 weeks) after the end of study treatment.

- Refrain from donating sperm for the duration of the study treatment and until 1 month (approximately 4 weeks) after the end of study treatment.

## **COLLECTION OF PREGNANCY INFORMATION**

Guidance for collection of Pregnancy Information and outcome of pregnancy on the Pregnancy Surveillance Form is provided in [Section 9.2.5](#) and the Appendix for Adverse Events and Serious Adverse Events Definitions and procedures for Evaluating, Follow-up and Reporting

## **APPENDIX 5            MANAGEMENT ALGORITHMS FOR STUDIES UNDER CTCAE VERSION 4.0**

These general guidelines constitute guidance to the Investigator and may be supplemented by discussions with the Medical Monitor representing the Sponsor. The guidance applies to all immuno-oncology agents and regimens.

A general principle is that differential diagnoses should be diligently evaluated according to standard medical practice. Non-inflammatory etiologies should be considered and appropriately treated.

[figure not shown]
Corticosteroids are a primary therapy for immuno-oncology drug-related adverse events. The oral equivalent of the recommended IV doses may be considered for ambulatory patients with low-grade toxicity. The lower bioavailability of oral corticosteroids should be taken into account when switching to the equivalent dose of oral corticosteroids.

Consultation with a medical or surgical specialist, especially prior to an invasive diagnostic or therapeutic procedure, is recommended.

The frequency and severity of the related adverse events covered by these algorithms will depend on the immuno-oncology agent or regimen being used.

## GI Adverse Event Management Algorithm

Rule out non-inflammatory causes. If non-inflammatory cause is identified, treat accordingly and continue I-O therapy. Opiates/narcotics may mask symptoms of perforation. Infliximab should not be used in cases of perforation or sepsis.

[figure not shown]

Patients on IV steroids may be switched to an equivalent dose of oral corticosteroids (e.g. prednisone) at start of tapering or earlier, once sustained clinical improvement is observed. Lower bioavailability of oral corticosteroids should be taken into account when switching to the equivalent dose of oral corticosteroids.

28-Sep-2020

## Renal Adverse Event Management Algorithm

Rule out non-inflammatory causes. If non-inflammatory cause, treat accordingly and continue I-O therapy.

[figure not shown]

Patients on IV steroids may be switched to an equivalent dose of oral corticosteroids (e.g. prednisone) at start of tapering or earlier, once sustained clinical improvement is observed. Lower bioavailability of oral corticosteroids should be taken into account when switching to the equivalent dose of oral corticosteroids.

28-Sep-2020

## Pulmonary Adverse Event Management Algorithm

Rule out non-inflammatory causes. If non-inflammatory cause, treat accordingly and continue I-O therapy. Evaluate with imaging and pulmonary consultation.

[figure not shown]

Patients on IV steroids may be switched to an equivalent dose of oral corticosteroids (e.g. prednisone) at start of tapering or earlier, once sustained clinical improvement is observed. Lower bioavailability of oral corticosteroids should be taken into account when switching to the equivalent dose of oral corticosteroids

28-Sep-2020

## Hepatic Adverse Event Management Algorithm

Rule out non-inflammatory causes. If non-inflammatory cause, treat accordingly and continue I-O therapy. Consider imaging for obstruction.

[figure not shown]
Patients on IV steroids may be switched to an equivalent dose of oral corticosteroids (e.g. prednisone) at start of tapering or earlier, once sustained clinical improvement is observed. Lower bioavailability of oral corticosteroids should be taken into account when switching to the equivalent dose of oral corticosteroids.

\*The recommended starting dose for grade 4 hepatitis is 2 mg/kg/day methylprednisolone IV.

28-Sep-2020

## Endocrinopathy Adverse Event Management Algorithm

Rule out non-inflammatory causes. If non-inflammatory cause, treat accordingly and continue I-O therapy. Consider visual field testing, endocrinology consultation, and imaging.

[figure not shown]

Patients on IV steroids may be switched to an equivalent dose of oral corticosteroids (e.g. prednisone) at start of tapering or earlier, once sustained clinical improvement is observed. Lower bioavailability of oral corticosteroids should be taken into account when switching to the equivalent dose of oral corticosteroids.

28-Sep-2020

## Skin Adverse Event Management Algorithm

Rule out non-inflammatory causes. If non-inflammatory cause, treat accordingly and continue I-O therapy.

Patients on IV steroids may be switched to an equivalent dose of oral corticosteroids (e.g. prednisone) at start of tapering or earlier, once sustained clinical improvement is observed. Lower bioavailability of oral corticosteroids should be taken into account when switching to the equivalent dose of oral corticosteroids.

[figure not shown]
\*Refer to NCI CTCAE v4 for term-specific grading criteria.

^If SJS/TEN is suspected, withhold I-O therapy and refer patient for specialized care for assessment and treatment. If SJS or TEN is diagnosed, permanently discontinue I-O therapy.

28-Sep-2020

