### **7.4.4 Dose Delay Criteria**

#### **7.4.4.1 Nivolumab**

Nivolumab administration should be delayed for the following:

- Grade 2 non-skin, drug-related AE, with the exception of fatigue
- Grade 2 drug-related creatinine, AST, ALT and/or Total Bilirubin abnormalities
- Grade 3 skin, drug-related AE
- Grade 3 drug-related laboratory abnormality, with the following exceptions:
  - Grade 3 lymphopenia or asymptomatic amylase or lipase elevations does not require dose delay
  - Grade  $\geq 3$  AST, ALT, or Total Bilirubin will require dose discontinuation (see [Section 8.1.1](#))
- Severe acute respiratory syndrome coronavirus 2 (SARS-CoV-2) infection, either confirmed or suspected
- Any adverse event, laboratory abnormality, or intercurrent illness which, in the judgment of the investigator, warrants delaying the dose of study medication.

Participants who require delay of nivolumab should be re-evaluated weekly or more frequently if clinically indicated and resume nivolumab dosing when re-treatment criteria are met.

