**7.4.5 Criteria to Resume Dosing****7.4.5.1 Nivolumab**

Participants may resume treatment with study treatment when the drug-related AE(s) resolve to Grade  $\leq$  1 or baseline value, with the following exceptions:

- Participants may resume treatment in the presence of Grade 2 fatigue
- Participants who have not experienced a Grade 3 drug-related skin AE may resume treatment in the presence of Grade 2 skin toxicity
- For participants with Grade 2 AST, ALT and/or Total Bilirubin Abnormalities, dosing may resume when laboratory values return to baseline and management with corticosteroids, if needed, is complete.
- Drug-related pulmonary toxicity, diarrhea or colitis must have resolved to baseline before treatment is resumed. Participants with persistent Grade 1 pneumonitis after completion of a steroid taper over at least 1 month may be eligible for retreatment if discussed with and approved by BMS Medical Monitor (or designee).

- Participants with SARS-CoV-2 infection (either confirmed or suspected) may resume treatment if they meet all of the following:
  - At least 10 days (20 days for severe/critical illness) have passed since symptoms first appeared or positive test result (eg, reverse transcription-polymerase chain reaction [RT-PCR] or viral antigen)
  - Resolution of acute symptoms (including at least 24 hours has passed since last fever without fever reducing medications)
  - Evaluation by the Investigator with confirmation that there are no sequelae that would place the participant at a higher risk of receiving investigational treatment
  - Consultation with the Medical Monitor or designee. For suspected cases, treatment may also resume if SARS-CoV-2 infection is ruled out and other criteria to resume treatment are met

Participants with drug-related endocrinopathies adequately controlled with only physiologic hormone replacement may resume treatment after consultation with the BMS Medical Monitor (or designee). Adrenal insufficiency requires discontinuation regardless of control with hormone replacement.

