#### **7.4.6 Management Algorithms**

Immuno-oncology (I-O) agents are associated with AEs that can differ in severity and duration than AEs caused by other therapeutic classes. Nivolumab and BMS-986205 are considered as immuno-oncology agents in this protocol. Early recognition and management of AEs associated with immuno-oncology agents may mitigate severe toxicity. Management algorithms have been developed to assist investigators in assessing and managing the following groups of AEs:

- Gastrointestinal
- Renal
- Pulmonary (For participants with dyspnea, CBC and methemoglobin should be measured)
- Hepatic
- Endocrinopathy
- Skin
- Neurological (For participants with confusion, methemoglobin should be measured)
- Myocarditis

The above algorithms are found in the [Appendix 5](#) of this protocol.

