### **8.1.1 Discontinuation of Nivolumab**

Nivolumab treatment should be permanently discontinued for the following:

- Any Grade 2 drug-related uveitis, eye pain or blurred vision that does not respond to topical therapy and does not improve to Grade 1 severity within the time frame permitted for dose delays OR requires systemic treatment

- Any Grade 3 non-skin, drug-related AE lasting > 7 days or recurs, with the following exceptions for laboratory abnormalities, drug-related uveitis, pneumonitis, bronchospasm, neurologic toxicity, hypersensitivity reactions, infusion reactions, and endocrinopathies:
  - Grade 3 drug-related uveitis, pneumonitis, bronchospasm, neurologic toxicity, hypersensitivity reaction, or infusion reaction of any duration requires discontinuation.
  - Grade 3 drug-related endocrinopathies, adequately controlled with only physiologic hormone replacement do not require discontinuation. Adrenal insufficiency requires discontinuation regardless of control with hormone replacement.
  - Grade 3 drug-related laboratory abnormalities do not require treatment discontinuation except:
    - ◆ Grade 3 drug-related thrombocytopenia > 7 days or associated with bleeding requires discontinuation
    - ◆ Grade  $\geq$  3 drug-related AST, ALT or total bilirubin requires discontinuation\*
    - ◆ Concurrent AST or ALT > 3 x ULN and total bilirubin > 2x ULN
- \*In most cases of Grade 3 AST or ALT elevation, study treatment(s) will be permanently discontinued. If the investigator determines a possible favorable benefit/risk ratio that warrants continuation of study treatment(s), a discussion between the investigator and the BMS Medical Monitor/designee must occur.
- Any Grade 4 drug-related AE or laboratory abnormality (including but not limited to creatinine, AST, ALT, or Total Bilirubin), except for the following events which do not require discontinuation:
  - Grade 4 neutropenia  $\leq$  7 days
  - Grade 4 lymphopenia or leukopenia or asymptomatic amylase or lipase
  - Isolated Grade 4 electrolyte imbalances/abnormalities that are not associated with clinical sequelae and are corrected with supplementation/appropriate management within 3 calendar days of their onset

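### For a drug-related SJS or TEN event graded 3, Appendix 5 stops nivolumab and BMS-986205 permanently, while Sections 7.4.4, 7.4.5 and 8.1.1 provide only for delay and possible resumption

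*Combined protocol and SAP*

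**What the plan says.** **Appendix 5, Skin Adverse Event Management Algorithm.** The footnote has two parts. On suspicion: "If SJS/TEN is suspected, withhold I-O therapy and refer patient for specialized care for assessment and treatment". On diagnosis: "If SJS or TEN is diagnosed, permanently discontinue I-O therapy". The visible text attaches no grade to either part. The appendix opens by describing its own status: "These general guidelines constitute guidance to the Investigator". Section 7.4.6 refers sites to these algorithms and settles which drugs are meant: "Nivolumab and BMS-986205 are considered as immuno-oncology agents in this protocol".

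**Delay.** Section 7.4.4.1 lists "Grade 3 skin, drug-related AE" as a reason to delay nivolumab. Section 7.4.4.2 has the same entry for nivolumab plus BMS-986205. The matching row of Table 7.4.4.2-1 reads yes for nivolumab delay, yes for BMS-986205 delay and no for BMS-986205 reduction. After a delay, Section 7.4.4.1 says participants are to be re-evaluated and "resume nivolumab dosing when re-treatment criteria are met".

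**Resumption.** Sections 7.4.5.1 and 7.4.5.2 permit restarting once the drug-related event is at Grade 1 or below or at baseline. Their skin exception is: "Participants who have not experienced a Grade 3 drug-related skin AE may resume treatment in the presence of Grade 2 skin toxicity".

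**Permanent discontinuation.** The Grade 3 rule in Section 8.1.1 begins "Any Grade 3 non-skin, drug-related AE lasting > 7 days or recurs". A separate item stops nivolumab for any Grade 4 drug-related event, subject to listed exceptions.

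**The concern.** A site that manages a Grade 3 skin reaction from Sections 7 and 8 finds a delay followed by a permitted restart. If the reaction is diagnosed as SJS or TEN, a site that turns to Appendix 5 finds a permanent stop. SJS and TEN are named only in that footnote, in an appendix that calls itself guidance. They do not appear in the delay, resumption or discontinuation lists.

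This still matters after the decision to close the study. Section 3.1.2 lets participants on treatment continue, and lets those who had already consented and were in screening be randomized. Re-exposure after a potentially fatal reaction should not depend on which page a site consults.

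There is also a smaller reporting consequence. Adverse events leading to discontinuation remain a safety measure in Table 4-1, and the same clinical event could be counted there or not according to the text the site followed.

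**Working it through.** No arithmetic is involved and the plan states no figure on this point. The check follows a drug-related SJS or TEN event through each list by grade.

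| Situation | Sections 7.4.4, 7.4.5 and 8.1.1 | Appendix 5 footnote | Result |
|---|---|---|---|
| Grade 3, diagnosed | Delay; may resume at Grade 1 or below or baseline; outside the Grade 3 stopping rule | Permanent stop of nivolumab and BMS-986205 | Conflict |
| Grade 4, diagnosed | Permanent stop under the Grade 4 item of 8.1.1 | Permanent stop | Agreement |
| Suspected, below Grade 3 | No listed skin criterion, but the investigator may delay on judgment | Withhold and refer | No firm conflict shown |

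1. **Delay.** The Grade 3 skin entry in Sections 7.4.4.1 and 7.4.4.2 and in the table has no SJS/TEN carve-out.
2. **Resumption.** The skin exception removes one option: a participant who has had a Grade 3 skin event cannot restart while at Grade 2. The general rule then applies, so restart is open at Grade 1 or below or at baseline. SJS and TEN are not among the exceptions in either section.
3. **Stopping at Grade 3.** The Section 8.1.1 rule is confined to non-skin events, so a Grade 3 skin event is not a mandatory stop under it, whatever the diagnosis.
4. **Stopping at Grade 4.** The exceptions concern neutropenia, lymphopenia or leukopenia, amylase or lipase, electrolytes and endocrinopathies. None is a skin event, so the two texts agree.
5. **Other stopping clauses.** Section 8.1 has a best-interest stop. Section 8.1.1 has a substantial-risk stop, a stop for events needing 10 mg per day or more of prednisone or equivalent for more than 12 weeks, and a stop for delays over 10 weeks, with exceptions. Any of these could end treatment in a particular case. None names SJS or TEN, and none must apply to a Grade 3 case that recovers promptly.
6. **The other drugs.** BMS-986205 is covered directly by the Appendix 5 wording through Section 7.4.6, so the same conflict applies to it. Section 8.1.2 stops it by reference to Section 8.1.1, where SJS and TEN are absent. BCG is not listed as an immuno-oncology agent. Section 8.1.3 also points to Section 8.1.1, so neither text states an SJS/TEN rule for BCG.

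The protocol does write other event-specific stops into the body. Adrenal insufficiency is in both resumption sections and in Section 8.1.1, and serotonin syndrome is in Section 8.1.2.

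**The case against.** The strongest reply is that a site can obey both texts. The resumption rule says participants may restart; nothing compels it. The footnote is the more specific instruction, and the body leads readers to the algorithms: Section 7.4.6 points to Appendix 5, and Section 8.1.1 itself mentions them. A careful investigator would delay at Grade 3, read the algorithm and stop on diagnosis. That is fair, and it means the protocol does not order re-dosing after SJS or TEN. It remains true that one text permits what the other forbids.

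A second reply is that Amendment 04 supplies a precedence rule. Section 3.1.2 says its changes override existing requirements where they appear to differ. The change summary records updated algorithms, and the skin page is dated 28-Sep-2020, after Revised Protocol 03 of 01-Nov-2019. This supports reading Appendix 5 as controlling, but does not settle the matter. The clause is general, the same amendment also edited Sections 7.4.4 and 7.4.5, and it cannot be shown that the footnote was new.

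A reader might infer more than the documents support:

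- **That the conflict extends to suspected events at Grade 1 or 2.** Both delay lists end with an investigator-judgment item that accommodates withholding. The algorithm figure is not shown, so any grade attached to the footnote in the figure cannot be seen.
- **That investigator judgment is the only route to a stop below Grade 4.** The prolonged-steroid and long-delay clauses have no skin exclusion.
- **That the contradiction reaches all three drugs.** For BCG there is an omission, because Appendix 5 gives no BCG instruction to contradict.

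**Conclusion.** The point holds in a narrow form. For a drug-related SJS or TEN event graded 3, Appendix 5 requires permanent discontinuation of nivolumab and BMS-986205 on diagnosis, while Sections 7.4.4 and 7.4.5 provide for delay and possible resumption and Section 8.1.1 leaves the event out of its Grade 3 rule. There is no conflict at Grade 4.

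Its size cannot be stated as a number. The documents give neither the CTCAE grading of SJS or TEN nor their frequency, so the share of cases falling at Grade 3 is unknown. If these events are rare, which is an assumption here, the effect on discontinuation counts is small, and the planned safety analyses are descriptive (Section 10.3.2). The reason to act is participant safety while dosing continues, not bias in an estimate.

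The conclusion rests on the visible text of the skin algorithm page, whose figure is missing, and on the diagnosis clause of the footnote meaning what it says without a grade limit. It takes no position on which clinical rule is right.

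**What to change.** Reconcile the Appendix 5 SJS/TEN footnote with Sections 7.4.4.1, 7.4.4.2, 7.4.5.1, 7.4.5.2 and 8.1.1 and with Table 7.4.4.2-1, so that the same instruction appears in each. State whether Appendix 5 or Sections 7 and 8 governs when they differ, and how the Amendment 04 override in Section 3.1.2 applies. Clarify whether BCG is covered. The clinical team decides the content of the rule.

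The cost is a wording change by amendment or administrative letter, plus a memo to sites. No data collection, analysis or sample size is affected.
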